10.5 Data Analysis

This is a longitudinal observational study to compare effects of two treatment groups on the quality of life and to explore how the treatment effects are modified by T:B ratio. For each study patient, we have a data vector $D=(\text{group}, \text{T:B ratio}, \text{location}, Q(t), 3D(t), W)$, where group is a binary indicator for two comparison groups. T:B ratio is the tumor: breast ratio measured at a continuous scale, and location is a binary indicator of tumor location. $Q(t)$ and $3D(t)$ are Q score and the VECTRA 3D generated mammometrics respectively, measured as continuous variables at $t=(0,1,2)$, where $t=0$ is the pre-treatment baseline measurement. W is a set of patient characteristics – e.g., age, obesity, stage, etc. A longitudinal study generates correlations among the repeated measurements within the same individual, and observational study often comes with a biased estimate of the treatment comparison due to confounding. These two issues, the correlation of repeated measurements and confounding, must be taken into account in the data

analysis. Regression analyses of correlated data can simultaneously address these two issues. There are two families of statistical methods for regression analyses of correlated data – mixed effect model and generalized estimating equation (GEE). Both are appropriate for our study, even though the interpretations are different – population average vs subject specific. Data analyses for our study will be performed within this framework to adjust for the patient characteristics for unbiased comparison of treatment effect and to take into account the correlations.

10.5.1 Primary objectives:

For main effect of treatment group on Q-score: fit and test a model with Q score as the dependent variable and group as the independent variable, controlling for W in the model – (Model 1).

For the difference in Q score between two treatment groups modified by T:B ratio: fit and test a model with Q score as the dependent variable, and group, T:B ratio, and group-by-T:B ratio interaction as the independent variables, controlling for W in the model – (Model 2). The results can be better presented as a graph with two lines – Q score as a function of T:B ratio for those treated with BCT, and for those treated with Mastectomy+reconstruction.

10.5.2 Secondary objectives:

Does tumor location impact the influence of tumor: breast ratio on patient reported outcomes following mastectomy with reconstruction or BCT?

- Add location and three way interaction term –group-by-T:B ratio-by-location into Model 2 – (Model 3). The results can be better presented as two graphs – one for each location. See Model 2 for the graph.

How does the pre and post-op Breast Q for the two groups (mastectomy + recon vs. BCT) reflect the tumor: breast ratio as calculated from 3D images rendered from MRI utilizing software-based algorithms?

- Fit and test a model with Q-score as the dependent variable and 3D image data as the independent variable with appropriate non-linear terms for 3D (e.g. spline functions), with group and possible interaction of group-by-3D (Model 4).

How does the pre and post-op Breast Q for the two groups (mastectomy + recon vs. BCT) reflect the VECTRA 3D generated mammometrics?

- Both the Breast Q and the VECTRA 3 D generated mammometrics are continuous variables. The correlation between them will be quantified by Pearson or Spearman correlation coefficient with one sample t test for population correlation coefficient =0, and with Fisher Z transformation to test the population correlation coefficient not equal to zero.

What is the impact of radiation in BCT on Breast Q (Q-score before and after

radiotherapy) and VECTRA (breast volume, nipple position, total breast skin surface area before and after radiotherapy)?

- Perform the subgroup analyses of BCT patients comparing change in outcomes of interest before and after radiation.

How do complications that arise from each scenario (mastectomy + recon) vs. BCT impact patient satisfaction?

- Fit and test a model with Q-score as the dependent variable and complication and group, and possible group-by-complication interaction as independent variables controlling for W in the model.

What is the impact of tumor location and obesity as independent determinants of patient satisfaction in the two groups (mastectomy + recon vs. BCT) relative to tumor: breast ratio?

- Fit and test a model with Q-score as the dependent variable and group, T:B ratio, location, and obesity as the independent variables, controlling for W in the model. Obtain the standardized regression coefficients for location, obesity, and T:B ratio, and compare each other to determine their relative importance.

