2.2 Secondary Objectives

- Does tumor location impact the influence of tumor: breast ratio on patient reported outcomes following mastectomy with reconstruction or BCT?
- How does the pre and post-op Breast Q for the two groups (mastectomy + recon vs. BCT) reflect the tumor: breast ratio as calculated from 3D images rendered from MRI utilizing software-based algorithms?
- How does the pre and post-op Breast Q for the two groups (mastectomy + recon vs. BCT) reflect the VECTRA 3D generated mammometrics?

- What is the impact of radiation in BCT on Breast Q (Q-score before and after radiotherapy) and VECTRA (breast volume, nipple position, total breast skin surface area before and after radiotherapy)?
- How do complications that arise from each scenario (mastectomy + recon) vs. BCT impact patient satisfaction?
- What is the impact of tumor location and obesity as independent determinants of patient satisfaction in the two groups (mastectomy + recon vs. BCT) relative to tumor: breast ratio?

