10.0 STATISTICAL CONSIDERATIONS

10.1 Outcome Measures

- Tumor: breast ratio generated from MRI
- The Breast Q (pre and post op) outcome measurements
- Breast mammometrics generated from 3D imaging

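### Models 1 and 2 name no primary visit, no visit or group-by-visit term and no role for baseline Q, so the primary group effect is an unspecified average over visits

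*Combined protocol and SAP*

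**What the plan says.** Section 10.5 defines Q(t) at t=0, 1 and 2, and says that t=0 "is the pre-treatment baseline measurement". (Section 10.3 uses t=0 for the tumor operation; the 10.5 meaning is used here.) After naming the mixed effect model and GEE, it states: "Data analyses for our study will be performed within this framework".

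Section 10.5.1 then gives the primary models. Model 1 is to "fit and test a model with Q score as the dependent variable and group as the independent variable, controlling for W in the model". The regressors listed for Model 2 are "group, T:B ratio, and group-by-T:B ratio interaction as the independent variables, controlling for W in the model". On presentation, the plan adds: "The results can be better presented as a graph with two lines", one per treatment, with Q plotted against the T:B ratio. The adjustment set is open-ended and does not name baseline Q: "W is a set of patient characteristics – e.g., age, obesity, stage, etc".

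Two other places bear on which scores are outcomes. Section 10.1 lists "The Breast Q (pre and post op) outcome measurements". The secondary objective behind Model 3, which extends Model 2, concerns "patient reported outcomes following mastectomy with reconstruction or BCT".

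Under section 6.5, the first post-operative score (t=1) is taken 1 to 10 weeks after surgery, before radiotherapy in Group A and before reconstruction is complete in Group B. The final score (t=2) follows radiotherapy or the last reconstructive step.

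**The concern.** The plan does not itself treat the visits as interchangeable. One secondary objective asks how Q changes across radiotherapy in the BCT group, which is a change from t=1 to t=2 in one arm only. A group difference that is constant over visits therefore cannot be assumed, yet the listed models estimate a single one.

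The primary objective (section 2.1) asks at which T:B ratio patient-reported outcomes favour mastectomy with reconstruction. That answer is read from the two Model 2 lines, and the plan does not fix the visit to which they refer. It also leaves open whether baseline Q is an outcome, a covariate or the reference for change. In a non-randomised comparison these choices can give different answers.

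**Working it through.** **Inputs.** From section 10.4: 83 per arm, SD 20, a 10-point difference, two-sided alpha 0.05. Assumed here: within-patient correlation rho 0.5 (range 0.3 to 0.7), equal at all visit pairs; equal variances; complete data; no baseline difference; no W; a t=1 effect of none, half or all of the t=2 effect.

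**The plan's own figure.** With d=0.45 and 80% power, 83 per arm is reproduced by a Wilcoxon-Mann-Whitney calculation with a normal parent distribution (83 gives power 0.804; a t-test needs 79). This is a two-group, single-time-point calculation, and no visit is named for it.

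**What the listed coefficient estimates.** With no visit interaction it is a weighted average of the visit-specific group differences. On complete data the weights are equal under independence or exchangeable covariance with equal variances, and adding a visit main effect alone does not change the estimate. Under AR(1) the three-visit weights are proportional to 1, 1-rho, 1. At rho=0.5 that is 1, 0.5, 1, or 0.4/0.2/0.4. The plan names no covariance.

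**Size of the estimate, equal weights, 10 points at t=2:**
- t=1 and t=2 pooled: (0+10)/2=5.0; (5+10)/2=7.5; (10+10)/2=10.
- All three pooled: (0+0+10)/3=3.3; (0+5+10)/3=5.0; (0+10+10)/3=6.7.
- AR(1), rho 0.5, three visits: 0.4×10=4.0 for a t=2-only effect; 0.2×10+0.4×10=6.0 for a full effect at both post-operative visits.

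**SDs at rho=0.5.** Two-visit mean: 20×sqrt((1+rho)/2)=17.3. Three-visit mean: 20×sqrt((1+2rho)/3)=16.3. Baseline-adjusted t=2: 20×sqrt(1-rho²)=17.3.

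**Power (noncentral t, 83 per arm), with the range over rho 0.3 to 0.7:**

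| Contrast | t=1 effect none | half | full |
|---|---|---|---|
| t=1 and t=2 pooled | 46% (41-51) | 79% (74-85) | 96% (94-98) |
| t=0, 1, 2 pooled | 26% (22-31) | 50% (43-59) | 74% (67-83) |
| t=2 alone | 89% | 89% | 89% |
| t=2, baseline-adjusted | 96% (92-99) | 96% | 96% |

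The plan's d=0.45 on an SD of 20 is 9 points. At rho=0.5 the rows become 38/70/91%, 22/42/65%, 82% and 91%.

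**Crossing ratio.** Take the 0.2 hypothesised in section 1.2 as the true t=2 crossing, with an assumed t=2 difference (reconstruction minus BCT) of -8+40T and an assumed t=1 difference of a+40T. With equal weights and no difference at t=0, the pooled crossing is T=(8-a)/80 whether or not t=0 is included. With the AR(1) weights and three visits it is T=(3.2-0.2a)/24.

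| a | equal weights | AR(1), three visits |
|---|---|---|
| -16 | 0.30 | 0.267 |
| -12 | 0.25 | 0.233 |
| -8 | 0.20 | 0.20 |
| -4 | 0.15 | 0.167 |

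There is no shift when t=1 also crosses at 0.2.

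**The case against.** The best defence is that the model statements are shorthand. The plan commits to a longitudinal framework that handles within-patient correlation, and the open-ended W could include baseline Q. But section 10.5 does write out interactions and spline terms where it wants them, and visit never appears. A silently assumed visit main effect would not help, because under equal weighting it leaves the group coefficient unchanged.

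Four stronger readings are tempting, and the documents do not support them.
- *That baseline Q is certainly analysed as an outcome.* Section 10.1 makes this possible, but it is a list of measures. Calling t=0 a baseline, and asking about outcomes after surgery, makes pooling t=1 and t=2 the more natural reading. The three-visit power figures are the less likely case.
- *That the effect is always diluted within fixed bounds.* The bounds need a t=1 effect between zero and the t=2 effect. With a=-16 and T=0.25, the differences are -6 at t=1 and +2 at t=2. The equal-weight pooled values are -2.0 (two visits) and -1.3 (three), so the sign is wrong. Conversely, with equal effects at both post-operative visits, pooling those two dilutes nothing.
- *That the crossing will be wrong.* It moves only if the other pooled visits move it.
- *That t=2 is the only legitimate target.* A time-averaged post-operative effect is a proper estimand if it is stated.

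The last three limit the size of the point; they do not supply the missing specification.

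**Conclusion.** The point holds and should be fixed. Models 1 and 2 do not define which group difference is tested, or the visit to which the Model 2 lines refer, and no other section fills the gap. As listed, the models pool t=1 with t=2, and possibly t=0 as well. The half-to-full and one-third-to-two-thirds ranges depend on equal weights, no baseline difference and a t=1 effect between zero and the t=2 effect. The power figures also depend on the assumed correlation. The size of any shift in the crossing ratio cannot be derived from the documents. Nothing here shows that 83 per arm is inadequate for a properly stated contrast in Model 1: t=2 alone has 89% power at 10 points with complete data.

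**What to change.** Change the SAP wording; all the scores are already collected.
- Fit the mixed model or GEE to t=1 and t=2 with visit and group-by-visit. In Model 2 also add T:B-by-visit and group-by-T:B-by-visit. Patients without a t=2 score still contribute.
- Enter baseline Q, with baseline-by-visit, as a covariate and not as an outcome. Use change from baseline as a sensitivity analysis where the pre- and post-operative modules share a scale.
- Name one primary contrast in advance. We recommend t=2, because the primary question concerns the finished result. A stated average of t=1 and t=2 is an acceptable alternative.
- Report the crossing T:B ratio for that contrast with a 95% CI, even if unbounded.

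This adds four coefficients to Model 1 and six to Model 2. The downsides are these.
- If effects are equal at t=1 and t=2, the average has more power than unadjusted t=2 (96% against 89% at rho=0.5).
- The Model 2 interaction has SE of about SD×sqrt(2/83)/(SD of T:B). With an assumed T:B SD of 0.10 and rho=0.3, this is 19.1×0.155/0.10=30 for baseline-adjusted t=2 and 16.1×0.155/0.10=25 for the post-operative average. At rho=0.5 the two are equal.
- Baseline adjustment does not reduce bias under every imbalance. With no treatment effect, no W and rho=0.5, a 5-point imbalance at t=0 only gives a bias of -5×0.5=-2.5, where unadjusted t=2 has none. The same imbalance at every visit gives 5×(1-0.5)=2.5, against 5 unadjusted.
- The timing of t=2 differs between groups, so report actual time since final treatment by group.

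Separately, section 6.5 sets the Group B final visit at 3 to 8 months from the last reconstructive operation, while section 10.3 requires 6 months or more from the last treatment or reconstructive step. These passages must be reconciled.

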1.0 BACKGROUND AND RATIONALE

1.1 Background

Patients with localized ductal carcinoma in situ (DCIS) and Stage I-IIIA breast cancers are usually candidates for either breast conservation therapy (BCT: lumpectomy with radiation) or mastectomy since survival outcomes are comparable. By its very name, BCT implies superior aesthetic outcomes as breast tissue is preserved. Not surprisingly, when offered, the majority of women will choose BCT over mastectomy with reconstruction, (~65% BCT vs. 35% with mastectomy of which <30% of those receive a reconstruction).

The degree of tissue loss with BCT however falls on a spectrum that is influenced by tumor size and the variable impact of radiation therapy. Large-breasted women are able to absorb a larger absolute tumor resection than smaller breasted women due to the relative size of their breast. Further, the majority of women note that the upper-inner pole of their breast is more aesthetically relevant than other quadrants. Therefore, BCT impacting this region may create a relatively greater degree of dissatisfaction. A recent survey performed by the American Society of Plastic Surgeons found that ~ 46% of women undergoing BCT were disappointed with their results. In another survey – the Breast Cancer Treatment and Outcomes Survey – increased breast asymmetry following BCT was correlated with depressed mood and a feeling of stigmatization. In another study, tumors involving >10% of breast volume, and particularly those located in the medial breast, were associated with decreased patient satisfaction. Unfortunately, quantification of tumor: breast ratio was imprecisely calculated, and patient satisfaction was not determined by a validated, breast-specific patient reported outcomes tool in any of these studies.

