1.2 Rationale

This study will show that many patients currently selected for lumpectomy will have better aesthetic outcomes when mastectomy with reconstruction is chosen. While the absolute dimensions of a breast cancer are relevant to staging and treatment, tumor: breast ratio is a key factor in determining patient satisfaction with lumpectomy, and in turn should determine when a mastectomy with reconstruction should be performed to yield an optimal result. It is the relative size of the tumor and volume of its resection that will profoundly impact breast symmetry and therefore impact patient reported outcomes following BCT. Tumor: breast ratios > 0.2 will be associated with progressively poorer patient satisfaction outcomes when treated with BCT than would be provided by mastectomy with reconstruction. Tumors in the superomedial breast will be even more sensitive to tumor: breast ratio. We hypothesize that BCT will be particularly sensitive to tumor: breast ratio whereas mastectomy with reconstruction will be less dependent. The results from this study will enable plastic and oncologic surgeons to identify a new cohort of patients, previously destined for BCT, to undergo a mastectomy with reconstruction to optimize their overall satisfaction with the aesthetic outcomes with equivalent treatment of their disease.

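### Primary Model 1 omits T:B ratio and tumour location, and Model 2 omits location, so the non-randomised comparison is open to confounding by two factors the protocol itself ties to satisfaction

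*Combined protocol and SAP*

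**What the plan says.** Section 10.5 acknowledges that an "observational study often comes with a biased estimate of the treatment comparison due to confounding", and sets the regression framework the task "to adjust for the patient characteristics for unbiased comparison of treatment effect". The data vector in that section has separate entries for group, T:B ratio, location, the Q score, the 3D measurements and W. On W it says: "W is a set of patient characteristics – e.g., age, obesity, stage, etc".

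Section 10.5.1 has two models under the primary objectives. For Model 1 the instruction is to "fit and test a model with Q score as the dependent variable and group as the independent variable, controlling for W in the model". By contrast, Model 2 has group, T:B ratio, their interaction and W. Location first enters in Section 10.5.2, where Model 3 adds it to Model 2. It appears again in the last secondary model, together with group, T:B ratio, obesity and W.

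On what these variables do, Section 1.2 states that "tumor: breast ratio is a key factor in determining patient satisfaction with lumpectomy" and expects superomedial tumours to be more sensitive to it. Section 1.1 reports that "tumors involving >10% of breast volume, and particularly those located in the medial breast, were associated with decreased patient satisfaction". Section 2.2 asks about location as an independent determinant of satisfaction. Section 6.7 confirms that the study observes usual care.

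**The concern.** In a comparison without randomisation, a variable that predicts the outcome and differs between arms biases the group coefficient unless it is adjusted for. Model 1 leaves out the two outcome predictors that the protocol stresses most. The open end of the W list does not bring them in, because Models 2 and 3 introduce T:B ratio and location as new terms.

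Stage and obesity in W are partial proxies only. Section 1.2 itself separates absolute tumour dimensions, which bear on staging, from the ratio. Stage carries neither breast volume nor location.

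Model 1 is listed first, is labelled the main effect of treatment, and is the contrast closest to the two-group mean difference on which Section 10.4 sizes the study. If the arms differ in T:B ratio or location given W, part of a tumour effect would be reported as an effect of the operation.

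**Working it through.** **1. The plan's own figure.** Section 10.4 gives d = 0.45, two-sided α = 0.05, power 0.80 and 83 per arm. The normal formula gives 78 and the two-sample t test 79. A Wilcoxon-Mann-Whitney calculation with a normal parent distribution gives 83, at power 0.804. The test is not named, so this match is inferred. (The stated 10 points over an SD of 20 is d = 0.50, not 0.45. That is a separate matter and does not affect this point.) Below, n = 83 per arm and SD = 20, so the standard error of the unadjusted difference is 20 × √(2/83) = 3.10 points.

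**2. Terms in each model.**

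| Model | Status | T:B ratio | Location |
|---|---|---|---|
| 1 | primary | no | no |
| 2 | primary | yes, with group interaction | no |
| 3 | secondary | yes | yes |
| Last model in 10.5.2 | secondary | yes | yes |

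**3. Bias from omitting T:B ratio, same slope in both arms.** Bias = b × s, where b is Q points lost per SD of T:B ratio and s is the between-arm difference in SD units given W. The documents give neither, so both are assumed.

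| b | s = 0 | s = 0.25 | s = 0.5 | s = 0.75 | s = 1 |
|---|---|---|---|---|---|
| 2 | 0 | 0.5 | 1.0 | 1.5 | 2.0 |
| 4 | 0 | 1.0 | 2.0 | 3.0 | 4.0 |
| 6 | 0 | 1.5 | 3.0 | 4.5 | 6.0 |

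With no true effect, the chance that Model 1 rejects is 0.05 at zero bias, 0.098 at 2 points, 0.249 at 4 and 0.485 at 6.

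**4. Simulation, same slope in both arms.** Assumed: 83 per arm, W = obesity and size-based stage, 10 points lost per 0.1 of T:B ratio, true group effect zero. If T:B ratio does not influence the choice of operation, the bias is 0. Where it does, with more large ratios in the reconstruction arm, Model 1 shows a false effect of about 1 to 4 points against reconstruction. In one set of four scenarios it was 1.4 to 3.4 points. This rose to 2.4 to 4.3 when a superomedial location (assumed 25% prevalence, 8 points) also affected choice. Halving the slope roughly halved the bias, to 0.9 to 1.9 points in one run.

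**5. Slope mainly in the BCT arm, as Section 1.2 hypothesises.** Take the extreme case. BCT loses b points per SD of T:B ratio, reconstruction loses none, and the reconstruction arm's mean ratio is s SD higher. Let g be the benefit of reconstruction at a ratio of zero SD, and m the BCT mean in SD units. Ignoring W:
- Model 1 estimates g + b·m.
- The true effect in women like the BCT arm is g + b·m, so the bias for that target is zero.
- The true effect in the pooled population (equal arms) is g + b·(m + s/2), so Model 1 is short by b·s/2: 1 point at b = 4, s = 0.5, and 3 points at b = 6, s = 1.

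Simulations with a reconstruction slope of 0 or 30% of the BCT slope agree. Model 1 fell within 0.9 points of the effect among BCT patients and 1.1 to 3.7 points short of the pooled effect.

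**6. Is an additive T:B term enough?** In the case of step 5, let v0 and v1 be the variances of T:B ratio in the BCT and reconstruction arms. The fitted common slope is −b·v0/(v0 + v1), and the group coefficient is short of the pooled effect by b·s·(1/2 − v0/(v0 + v1)). This vanishes only if the two variances are equal. In the simulations with unequal slopes the additive model still missed the pooled effect by 0.6 to 3.0 points. Model 2 averaged over the pooled T:B distribution gave a bias of 0.0 in the runs with T:B ratio acting in the BCT arm only.

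**7. Precision after adding T:B ratio.** The variance inflation is 1/(1 − r²) with r² = (s/2)²/(1 + (s/2)²). It is 1.06 at s = 0.5 and 1.25 at s = 1, so the standard error rises by about 3% and 12% before any gain from explained variance. Power for 9 points (d = 0.45) runs from 0.74 (s = 1, b = 2) to 0.86 (s = 0, b = 6), against 0.826 unadjusted. For 10 points it runs from 0.825 to 0.92.

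**The case against.** The strongest reply is that Model 1 is not the model that answers the question. Section 2.1 asks at which T:B ratio mastectomy with reconstruction is justified. Model 2 answers that, is also primary, and contains the ratio and its interaction with group. Two secondary models adjust for location as well. All of this stands. It narrows the gap in Model 2 to location, but leaves Model 1 as a primary comparison without either variable.

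A reader might infer that the protocol itself says T:B ratio and location drive the choice of operation, so that Model 1 is confounded by indication as a matter of record. The documents do not support that. Section 1.2 says the ratio ought to govern when mastectomy with reconstruction is done, which is a recommendation, and it expects many women now selected for lumpectomy to do better with the alternative. Nothing is said about location and choice. The link is plausible, since Section 1.1 notes that larger breasts absorb larger resections, but it is an inference.

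Sections 3.2 and 10.3 also restrict entry to women who could reasonably be considered for either approach. This limits imbalance without guaranteeing its absence. W is open-ended too, and if it balances both variables the bias is zero.

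Finally, a common slope in both arms runs against the protocol's own hypothesis. With the slope mainly in the BCT arm, Model 1 is close to right for women like those in that arm. That stands, and it means the size and direction of any error depend on a target population that Model 1 does not state.

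**Conclusion.** Should-fix. The text establishes that Model 1 omits T:B ratio and location, that Model 2 omits location, that the protocol treats both as determinants of satisfaction, and that treatment is not randomised. The comparison is open to confounding; bias is not demonstrated.

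The Model 1 bias is 0 if both variables are balanced given W, about 4 Q points at most in the simulations, and 6 at the far end of the wider range, against a design difference of 10. These figures rest on assumed slopes and imbalances that the documents do not supply, so none should be read as an expected bias. No figure was derived for the omission of location from Model 2.

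**What to change.** In Section 10.5.1:
- Model 1: Q score on group, T:B ratio, tumour location and W.
- Model 2: add location as a covariate.
- List the members of W in full.
- Because the T:B effect is expected to differ by arm, report the overall treatment contrast as the Model 2 prediction averaged over a stated target population, for example the pooled distribution of T:B ratio and location (g-computation). The additive group coefficient alone does not generally estimate that quantity.
- Show the distribution of T:B ratio by arm, so that readers can see where the arms overlap and where the contrast is extrapolated.

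Section 10.2 already provides for recording both variables, so no new data are needed. The cost is a few sentences, about two degrees of freedom in Model 1 and one in Model 2, and possibly a slightly wider interval. The change should be made before the analysis is run.

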10.4 Sample Size

Mammometrics will be converted to comparable data and then related to Q-Score as these are expected to be complex relationships.

We anticipate enrolling 83 subjects per study arm (166 total) with up to an additional 20 subjects undergoing mastectomy without reconstruction as a negative control for a total of 186 patients.

Initial plan is to use G*Power v 3.1, or a comparable statistical package. Based on an effect size $d=0.45$, Type I error $\alpha=0.05$, and power $(1-\beta) =0.8$, normal distribution, and 2-tails, we will require 83 subjects per arm (166 total). Assumptions: A difference in mean scores of 10 on a 100-point scale (Q-Score generated from Breast Q) was assumed to be significant. This is determined by assuming an SD of 20, with one-half of an SD being the threshold of discrimination for change in health-related quality of life.

Sample size calculations are based on 1) previously reported sample size calculations where data from the Breast Q for Breast Reconstruction was used with 2) the open-source statistical package G*Power 3.1.

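### Model 2 assumes Q score is linear in tumor:breast ratio and never checks it, so the threshold that the primary objective asks for can be biased in either direction

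*Combined protocol and SAP*

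**What the plan says.** Section 2.1 asks at which T:B ratio patient-reported outcomes justify mastectomy with reconstruction over BCT, so the answer is a point on the T:B axis. Section 10.5 treats T:B as continuous. In 10.5.1, Model 2 regresses Q score on "group, T:B ratio, and group-by-T:B ratio interaction as the independent variables", controlling for patient characteristics, and proposes a graph with one line per treatment group. It lists no spline, hinge or quadratic term and no test of linearity. It also gives no rule for reading a ratio off the graph. Model 3 (10.5.2) adds location terms to Model 2 and inherits its form.

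Section 1.2 states the expectation: "Tumor: breast ratios > 0.2 will be associated with progressively poorer patient satisfaction outcomes when treated with BCT", compared with mastectomy plus reconstruction. It adds that BCT should depend on T:B more strongly than reconstruction does.

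Non-linearity is foreseen once, in secondary Model 4: "with appropriate non-linear terms for 3D (e.g. spline functions".

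**The concern.** When the answer is a location on the covariate axis, the assumed shape in that covariate largely determines it. Suppose BCT satisfaction holds up to some ratio and then falls. A least-squares line cannot follow that. It averages the flat and falling parts, and meets the reconstruction line somewhere other than where the true curves meet.

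Section 1.2 says the results will identify patients, previously destined for BCT, for mastectomy with reconstruction. A misplaced threshold would assign patients to the wrong side of that line. The plan provides for curvature in a secondary model but not in the one that carries the primary question.

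**Working it through.** **Inputs from the documents.** Section 10.4 gives the arm size and SD: "Based on an effect size $d=0.45", "normal distribution, and 2-tails, we will require 83 subjects per arm (166 total", and "assuming an SD of 20, with one-half of an SD being the threshold of discrimination for change". The figure of 83 reproduces:

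- Normal approximation: 2 × (1.960 + 0.842)² / 0.45² = 77.5, so 78 per arm. The t-test needs 79.
- Wilcoxon–Mann–Whitney with a normal parent: 79 × π/3 = 82.7, so 83.

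(Ten points over an SD of 20 is d = 0.50, not 0.45. That is a separate matter.) The plan gives no figure for the crossover or its precision, and none for the T:B distribution.

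**Estimator.** With Q = β0 + β1·group + β2·TB + β3·group·TB, the lines cross at TB* = −β1/β3. This is the natural reading of 2.1 with the two-line graph, but the plan does not name it.

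**Assumed bend.** BCT: Q = P − b·max(TB − 0.2, 0). Reconstruction: Q = P − D, flat. The true crossover is 0.2 + D/b. The least-squares line for BCT is P + b(A − m·TB), so Model 2 reads (A + D/b)/m.

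**By hand, TB uniform on 0–0.4.**

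- Variance of TB = 0.4²/12 = 0.01333.
- Mean of max(TB − 0.2, 0) = 0.05; its covariance with TB = 0.01667 − 0.2 × 0.05 = 0.00667.
- m = 0.00667/0.01333 = 0.5, and A = −0.05 + 0.5 × 0.2 = 0.05.
- Model 2 reads 0.1 + 2D/b, against a truth of 0.2 + D/b. The two agree only at 0.30. Below that the line reads low, and above it high.

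**Other assumed distributions (large sample).** Entries are the Model 2 reading.

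| TB distribution | Share > 0.2 | True 0.20 | True 0.22 | True 0.25 | True 0.30 | True 0.35 | Sign changes at |
|---|---|---|---|---|---|---|---|
| Uniform 0–0.4 | 50% | 0.100 | 0.140 | 0.200 | 0.300 | 0.400 | 0.300 |
| Uniform 0–0.6 | 67% | 0.120 | 0.147 | 0.188 | 0.255 | 0.323 | 0.429 |
| Beta, mean 0.25 | 60% | 0.144 | 0.171 | 0.211 | 0.278 | 0.346 | 0.362 |
| Beta, mean 0.20 | 44% | 0.122 | 0.154 | 0.203 | 0.284 | 0.365 | 0.326 |
| Beta, mean 0.15 | 26% | 0.103 | 0.149 | 0.219 | 0.334 | 0.450 | 0.274 |
| Beta, mean 0.10 | 11% | 0.073 | 0.158 | 0.284 | 0.496 | 0.707 | 0.239 |
| Beta, mean 0.05 | 0.5% | 0.043 | above 1 | above 1 | above 1 | above 1 | 0.203 |

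**Skewed (lognormal) TB.**

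- Log-SD 0.7, median 0.08 or 0.10 (9–16% above 0.2), gaps of 3–5 points, slopes 100–150: truth 0.22–0.25, reading about 0.13–0.21.
- Log-SD 0.9, medians 0.04–0.10, same gaps and slopes: reading 0.11–0.20.
- Log-SD 0.7, median 0.06: truth 0.25 reads 0.26, and truth 0.30 (gap 10, slope 100) reads about 0.44.

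**No bend.** If the truth is two straight lines crossing at 0.2, the median Model 2 estimate is 0.199–0.200.

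**At 83 per arm, SD 20** (covariates and repeated measures left out; a crossing searched for in 0–0.6; medians taken over runs that found one; hinge at 0.2 in the BCT arm):

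| Truth | TB distribution | Straight line | Hinge at 0.2 |
|---|---|---|---|
| 0.25 (D = 10, b = 200) | Uniform 0–0.4 | 0.202 | 0.250 |
| | Beta, mean 0.15 | 0.219 | 0.250 |
| | Beta, mean 0.20 | 0.205 | 0.251 |
| 0.35 (D = 15, b = 100) | Uniform 0–0.4 | 0.375 | 0.347 |
| | Beta, mean 0.10 | 0.353, none found in 56% | 0.307, none found in 29% |

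A further simulation at the same size, truth 0.25, gave median crossovers of 0.17–0.20 for the straight line, 0.23–0.25 for a linear spline with a knot at 0.2, and 0.18–0.25 for a 3-knot restricted cubic spline. The flexible fits had similar or narrower 5–95% ranges and no more missing crossovers.

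**The case against.** A reader might infer that the protocol itself hypothesises a plateau up to 0.2, so that Model 2 contradicts it. The text does not go that far. Section 1.2 compares the two groups above 0.2 and is silent on the shape below. Two straight lines crossing at 0.2 satisfy it, and its remark that BCT is the more sensitive treatment describes a slope difference, which Model 2's interaction captures. Section 1.1 cites lower satisfaction already above 10% of breast volume, which argues against a plateau to 0.2. This objection stands. The documents leave the shape open, which is a reason to check linearity and not evidence that it fails.

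A reader might also infer that the crossover is biased low as a rule. The tables show both signs, including at a 10-point gap, the difference that section 10.4 treats as meaningful.

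Sampling error is a fair counterweight. If 4–16% of patients exceed 0.2, that is 83 × 0.04 ≈ 3 to 83 × 0.16 ≈ 13 per arm. With lognormal TB (median 0.06, log-SD 0.8) and truth 0.25, the straight-line crossover had median 0.138 and a 5–95% range of −0.43 to 0.86. That is far wider than the bias. It supports reporting an interval, but it does not make the straight line safer.

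Model 4's splines do not fill the gap. That model sits under the question on MRI-derived T:B, but its regressor is 3D image data, and section 10.5 uses 3D for the VECTRA mammometrics. It is also secondary, with no threshold attached.

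**Conclusion.** The concern holds in limited form. The primary answer rests on an untested straight line in T:B. If BCT bends at 0.2, the reading is often about 0.05–0.08 low for true crossovers of 0.22–0.25; across the cases above that read low, the shortfall ran from about 0.03 (0.25 − 0.219) to 0.11 (0.22 − 0.11). If the arms are equal up to 0.2, so that the threshold is 0.2 itself, the reading was low in every distribution in the first table, at 0.04–0.14. It turns high when few patients exceed 0.2 or the crossover lies well above it. With two straight lines there is no bias.

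These sizes depend on assumed T:B distributions, gaps and slopes, and on the crossover being the intended estimator. The documents do not support a general claim of low bias, or a claim that Model 2 contradicts a stated hypothesis. This should be fixed before the threshold is estimated, but it does not invalidate Model 2 as a test of whether the slopes differ.

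**What to change.** In 10.5.1, keep linear Model 2 and add one pre-specified refit: a linear spline in T:B with a knot at 0.2, interacted with group, or a 3-knot restricted cubic spline interacted with group, with knot positions stated in advance. Knot placement matters. A restricted cubic spline is linear beyond its outer knots, so an outer knot below 0.2 could not show a bend there.

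Then specify that:

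- the crossover is the quantity estimated, and it is reported from both fits whatever the result, with a confidence interval such as a bootstrap interval;
- the non-linear terms are tested and the result is reported;
- a threshold is stated only within the T:B range observed in both arms;
- if the two fits differ, the threshold is reported as model-dependent and does not rest on the straight line alone.

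This needs one more model on data already being collected, and about one extra parameter per arm. It does not cure sparse data: if few patients exceed 0.2, the crossover interval will be wide under either fit, and some analyses may find no crossover at all.
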